7.3 Importance of Adverse Event Reporting

Timely and complete reporting of safety information assists BerGenBio in identifying any untoward medical occurrence, thereby allowing:

- safety of study patients;
- a greater understanding of the overall safety profile of the investigational drug;
- recognition of dose-related investigational drug toxicity;
- appropriate modification of study protocols;
- improvements in study design or procedures; and

BerGenBio ASA
[name]
[name]
Norway

- adherence to worldwide regulatory requirements.

7.4 Evaluating Adverse Events

Following the patient's written consent to participate in the study, AEs occurring after consent, but before treatment, and during treatment and within 30 days after cessation of treatment are collected in accordance with [Section 7.1](#), [Section 7.4.3](#) and [Section 7.5](#).

All identified AEs must be accurately recorded and described on the appropriate AE page of the eCRF. If known, the diagnosis of the underlying illness or disorder should be recorded, rather than its individual symptoms. The following information should be captured for all AEs: date of onset and resolution, severity of the event (see definitions in [Section 7.4.1](#)), Investigator's opinion of the relationship to IMP (see definitions in [Section 7.4.2](#)) and assessment whether the event was serious or non-serious (see definitions in [Section 7.4.3](#)). In addition, treatment required for the AE, action taken with IMP, information regarding resolution/outcome.

7.4.1 Assessment of severity

All AEs (including SAEs) are to be accurately recorded on the AE page of the patient's eCRF. Each event will be graded for severity using the classifications of NCI CTCAE v5.0. For events not addressed in the NCI CTCAE v5.0, classifications the following grading will apply:

- **Mild (Grade 1)** - Mild; asymptomatic or mild symptoms; clinical or diagnostic observations only; intervention not indicated.
- **Moderate (Grade 2)** - Moderate; minimal, local or non-invasive intervention indicated; limiting age-appropriate instrumental activity of daily living.
- **Severe (Grade 3)** - Severe or medically significant but not immediately life-threatening; hospitalization or prolongation of hospitalization indicated; disabling; limiting self-care activity of daily living.
- **Life-threatening (Grade 4)** - Life-threatening consequences; urgent intervention indicated.
- **Death (Grade 5)** - Related to adverse event.

7.4.2 Assessment of relationship

All AEs (including SAEs) will be assessed for the relationship of the AE to both pembrolizumab and bemcentinib study drug using the following definitions:

- **Not/unlikely related** - The AE is not related if exposure to the investigational product has not occurred, *OR* the occurrence of the AE is not reasonably related in time, *OR* the AE is considered unlikely to be related to use of the investigational product because there are no facts (evidence) or arguments to suggest a causal relationship *AND* there is a possible alternative explanation.
- **Possibly related** - The administration of the investigational product and AE are considered reasonably related in time *AND* the AE could be explained by causes other than exposure to the investigational product.
- **Probably related** - Exposure to the investigational product and AE are reasonably related in time *AND* the investigational product is more likely than other causes to be responsible for the AE *OR* is the most likely cause of the AE.

BerGenBio ASA
[name]
[name]
Norway

- **Definitely related** - There is a reasonable temporal sequence between exposure to the investigational product and the AE, *OR* the event follows a known or expected response pattern to the investigational product, *AND* is confirmed by improvement on stopping the dosage of the investigational product. It may also be confirmed by reappearance upon repeated exposure where this is medically and ethically acceptable.

The relationship of the study treatment to an AE will be determined by the Investigator and subsequently reviewed by the medical monitor.

For reporting and data analysis purposes, AEs reported with a causality assessment of “Definitely”, “Probably”, and “Possibly” are to be considered as “having a reasonable causal relationship” to study drug. In case of disagreement between the Investigator and the Sponsor’s medical monitor, the more conservative assessment will determine the reportability of the case.

7.4.3 Immediate reporting of AEs and events of clinical interest to the Sponsor

7.4.3.1 Serious adverse events

An SAE is any untoward medical occurrence that at any dose (including overdose):

- Results in death.
- Is life-threatening:
 - “Life-threatening” means that the patient was at immediate risk of death at the time of the SAE; it does not refer to an SAE that hypothetically might have caused death if it were more severe.
- Requires hospitalization or prolongation of existing hospitalization:
 - This means that hospital inpatient admission or prolongation of hospital stay were required for the treatment of the SAE or that they occurred as a consequence of the event.
 - Visits to a hospital by ambulance or to the emergency room without admission will not be regarded as hospitalization unless the event fulfils any other of the serious criteria.
- Results in persistent or significant disability or incapacity:
 - “Persistent or significant disability or incapacity” means a permanent or significant and substantial disruption of a person’s ability to carry out normal life functions.
- Is a congenital anomaly or birth defect.
- Is an important medical event:
 - Medical and scientific judgment should be exercised in deciding whether expedited reporting is appropriate in situations where none of the outcomes listed above occurred. Important medical events that may not be immediately life-threatening or result in death or hospitalization but may jeopardize the patient or may require intervention to prevent one of the other outcomes listed in the definition above should also usually be considered serious. Examples of such events include allergic bronchospasm requiring intensive treatment in an emergency room or at home, blood dyscrasias, or convulsions that do not result in inpatient hospitalization, or the development of drug dependency or drug abuse.

BerGenBio ASA
[name]
[name]
Norway

Note: In addition to the above criteria, AEs meeting either of the below criteria, although not serious per International Council for Harmonisation (ICH) definition, are reportable to the Sponsor in the same timeframe as SAEs to meet certain local requirements.

Therefore, these events are considered serious by the Sponsor for collection purposes.

- Is a new cancer (that is not a condition of the study);
- Is associated with an overdose.

All patients with SAEs must be followed up for outcome.

For the time period beginning when the consent form is signed until treatment allocation, any SAE, or follow up to a SAE, including death due to any cause other than progression of the cancer under study, that occurs to any patient must be reported within 24 hours to the Sponsor if it causes the patient to be excluded from the trial, or is the result of a protocol-specified intervention, including but not limited to washout or discontinuation of usual therapy, diet, placebo treatment or a procedure.

For the time period beginning at treatment allocation through 90 days following cessation of treatment, or 30 days following cessation of treatment if the patient initiates new anticancer therapy, whichever is earlier, any serious adverse event, or follow up to a SAE, including death due to any cause other than progression of the cancer under study, whether or not related to the Sponsor's product, must be reported within 24 hours to the Sponsor either by electronic media or paper. Electronic reporting procedures can be found in the EDC data entry guidelines. Paper reporting procedures can be found in the Investigator Trial File Binder (or equivalent).

Additionally, any serious adverse event, considered by an investigator who is a qualified physician to be related to the Sponsor's product that is brought to the attention of the investigator at any time following consent through the end of the specified safety follow-up period specified in the paragraph above, or at any time outside of the time period specified in the previous paragraph also must be reported immediately to the Sponsor.

All patients with SAEs must be followed up for outcome.

7.4.3.2 Events of clinical interest

Selected non-serious and SAEs are also known as Events of Clinical Interest (ECI) and must be reported to the Sponsor.

For the time period beginning when the consent form is signed until treatment allocation, any ECI, or follow up to an ECI, that occurs to any subject must be reported within 24 hours to the Sponsor if it causes the subject to be excluded from the trial or is the result of a protocol-specified intervention, including but not limited to washout or discontinuation of usual therapy, diet, placebo treatment or a procedure.

For the time period beginning at treatment allocation through 30 days following cessation of treatment, any ECI, or follow up to an ECI, whether or not related to the Sponsor's product, must be reported within 24 hours to the Sponsor, either by electronic media or paper. Electronic reporting procedures can be found in the EDC data entry guidelines. Paper reporting procedures can be found in the Investigator Trial File Binder (or equivalent).

BerGenBio ASA
[name]
[name]
Norway

Events of clinical interest (ECI) for this trial include:

1. an overdose of Sponsor's product (either pembrolizumab or bemcentinib), as defined in [Section 7.6](#), that is not associated with clinical symptoms or abnormal laboratory results.
2. an elevated AST or ALT lab value that is greater than or equal to 3X the upper limit of normal and an elevated total bilirubin lab value that is greater than or equal to 2X the upper limit of normal and, at the same time, an alkaline phosphatase lab value that is less than 2X the upper limit of normal, as determined by way of protocol-specified laboratory testing or unscheduled laboratory testing*

*Note: These criteria are based upon available regulatory guidance documents. The purpose of the criteria is to specify a threshold of abnormal hepatic tests that may require an additional evaluation for an underlying etiology. The trial site guidance for assessment and follow up of these criteria can be found in the Guidance for Potential Drug-Induced Liver Injury (DILI) Cases Meeting Hy's Law Criteria held in the Investigator Trial File Binder (or equivalent).

7.4.4 Reporting SAEs and ECIs

Adverse events classified as SAEs or ECIs must be recorded on the designated eCRF page and require expeditious handling and reporting to the Drug Safety group at INC to comply with regulatory requirements.

The Principal Investigator (or designee) will notify INC within 24 hours of identifying an SAE or ECI, whether related or unrelated to investigational drug, by completing the SAE form and faxing the eCRF pages and any available supporting documentation to INC (see below for contact details).

When an overdose or drug misuse of either of the investigational products occurs with an adverse outcome, the Investigator should only complete the designated AE or SAE eCRF page. Expeditious handling and reported may be appropriate.

In the case of pregnancy, a separate 'pregnancy' and 'pregnancy outcome' form is used. However, the patient should be withdrawn from study treatment and appropriate follow up agreed with the Sponsor.

Table 19: Contact Details for SAE, ECI, New Cancer and Pregnancy/Lactation Reporting

[REDACTED]	[REDACTED]

BerGenBio ASA
[name]
[name]
Norway

7.4.5 Assessment of Expected Adverse Events

The Sponsor will assess all SAEs whether they are expected or unexpected. An unexpected AE is any adverse drug event considered to be at least possibly related to bemcentinib or pembrolizumab where the outcome, specificity, or severity of which is not consistent with those noted in the current IB for bemcentinib, or the Summary of Product Characteristics (SmPC) or Prescribing Information for pembrolizumab.

7.5 Reporting of Pregnancy or Lactation

Although pregnancy and lactation are not considered AEs, it is the responsibility of investigators or their designees to report any pregnancy or lactation in a patient (spontaneously reported to them) that occurs during the trial.

Pregnancies and lactations that occur after the consent form is signed but before treatment allocation/randomization must be reported by the investigator if they cause the patient to be excluded from the trial or are the result of a protocol-specified intervention, including but not limited to washout or discontinuation of usual therapy, diet, placebo treatment or a procedure.

Pregnancies and lactations that occur from the time of first dose of study treatment through to 120 days following cessation of Sponsor's product, or 30 days following cessation of treatment if the patient initiates new anticancer therapy, whichever is earlier, must be reported by the investigator. All reported pregnancies must be followed to the completion/termination of the pregnancy. Pregnancy outcomes of spontaneous abortion, missed abortion, benign hydatidiform mole, blighted ovum, fetal death, intrauterine death, miscarriage, and stillbirth must be reported as serious events (as Important Medical Events). If the pregnancy continues to term, the outcome (health of infant) must also be reported.

Pregnancies are to be reported using the same procedures/transmission methods as SAEs: the same fax numbers / email address / same SAE cover sheet. A study specific pregnancy form will be provided for pregnancy reporting.

7.6 Definition of Misuse and Overdose

Bemcentinib overdose is defined as any dose exceeding the loading dose (███████) of bemcentinib.

For this trial, a pembrolizumab overdose will be defined as ≥ 1000 mg (5 times the dose) of pembrolizumab. No specific information is available on the treatment of overdose of pembrolizumab. In the event of overdose, the subject should be observed closely for signs of toxicity. Appropriate supportive treatment should be provided if clinically indicated.

If the pharmacy discovers that an overdose has or may have been administered, they should contact the Study Investigator immediately. The Study Investigator will determine if the overdose is an Event of Clinical Interest (see [Section 7.4.3.2](#)).

7.7 Investigational Product Complaints

Pharmaceutical technical complaints associated with the investigational product must be reported to the Sponsor immediately. The same reporting timelines as for SAEs apply.

BerGenBio ASA
[name]
[name]
Norway

7.8 Reporting SAEs to the IRB or IEC

The Investigator must comply with the applicable regulatory requirements related to the reporting of SAEs to the IRB or local Institutional Ethics Committee (IEC). All SAEs that are related and unexpected must be reported by the Investigator (or alternative responsible person where specified in study delegation log) to the IEC/IRBs responsible for the study.

In such cases, the Drug Safety group will send the Principal Investigator a Council for International Organizations of Medical Sciences (CIOMS) or MedWatch form describing the event, for them to report to their IEC/IRB.

Other SAEs (i.e., expected or unrelated SAEs) should be reported per the relevant institution's procedures.

The Principal Investigator should also comply with the IEC/IRB procedures for reporting any other safety information. Where required, submission of Safety Updates by the Principal Investigator to Competent Authorities should be handled according to local regulations. The Principal Investigator must inform the Sponsor or their designated Clinical Research Organization (CRO) regarding these local requirements. Periodically (at least annually), the IB will be updated to include new and relevant safety information.

Until such time that an AE becomes identified in the bemcentinib IB, it should be considered unexpected in regard to bemcentinib causality, regardless of whether the AE has been the patient of a previous Safety Update.

7.9 Follow Up Information on an SAE

Collection of complete information concerning SAEs is extremely important. Thus, follow-up information that becomes available as the SAE evolves, as well as supporting documentation (e.g., hospital discharge summaries and autopsy reports), should be collected subsequently, if not available at the time of the initial report, and immediately sent using the same procedure as the initial SAE report. The original SAE form(s) must be kept on file at the study site. The Sponsor will also review SAE reports for missing information and send queries to the site for resolution as appropriate.

Appropriate diagnostic tests should be performed and therapeutic measures, if indicated, should be instituted. Appropriate consultation and follow-up evaluations should be carried out by the Principal Investigator (or designee). An SAE is followed until it is considered resolved, returns to baseline, is chronically ongoing, or is explained by the Principal Investigator.

7.10 Sponsor Reporting of SAEs

The Sponsor is responsible for reporting serious, study drug-related AEs/experiences to the Competent Authorities of the countries, the concerned IRBs/IECs participating in the clinical trial and the study Investigators. The Sponsor has assigned the drug safety group at INC to act on their behalf for safety submissions on this clinical study.

The Sponsor (or their delegated medical monitor) will determine whether expedited reporting is necessary for SAEs depending on the assessment of seriousness, expectedness, and relationship.

BerGenBio ASA
[name]
[name]
Norway

In case of disagreement between the Investigator and the Sponsor's medical monitor regarding causal relationship, the more conservative assessment will determine the reportability of the case.

The Sponsor, or their delegated CRO, will prepare Development Safety Update Reports (DSUR) and send the DSUR to the European Competent Authority(ies) and the US Authority(ies) where the trial is approved within the regulatory timeframe appropriate for the outcome of their assessment (see [Section 7.10.1](#) and [Section 7.10.2](#)). The assigned CRO will send the DSUR to the concerned IRB/IECs.

7.10.1 Expedited reporting

The Sponsor (or delegate) is responsible for the ongoing safety evaluation of the IMP. The assigned drug safety group is responsible for ensuring that expedited reports are made to all concerned Investigators, to the concerned IRB/IECs (where required), and to the relevant regulatory authorities of all adverse drug reactions that are both serious and unexpected, and of findings that could adversely affect the health of patients, impact on the conduct of the trial, or alter the Competent Authority's authorization to continue the trial.

In accordance with the US Code of Federal Regulations, Title 21 CFR Part 312.32, the European Directive 2001/20/EC, and the ICH Guidelines for Clinical Safety Data Management Definitions and Standards for Expedited Reporting, the Sponsor must submit written documentation in the form of an Investigational new drug (IND) Safety Report or suspected unexpected serious adverse reaction (SUSAR) reports, respectively. The Sponsor should submit to the Regulatory Authority all safety updates and periodic reports, as required by applicable regulatory requirements.

The drug safety group will assign a case number to be used in all future correspondence regarding the event.

All events qualifying as IND Safety Reports/SUSARs will be reported to the relevant regulatory authorities, IRB/IECs, and Investigators by the drug safety group. IND Safety Reports/SUSARs are required to be reported within 7 calendar days for life-threatening events and those resulting in death or 15 calendar days for all others. These timeframes begin with the first notification of the IND Safety Reports/SUSARs to the drug safety group from the Investigator.

7.10.2 Non-expedited reporting

All SAEs that do not require expedited reporting will be described in the interim safety reports.

BerGenBio ASA
[name]
[name]
Norway

8 DATA EVALUATION: CRITERIA FOR EVALUATION OF OBJECTIVES

8.1 Statistical Considerations, Interim Analysis and Sample Size

The study will employ a k -stage single-arm design, an approach derived from basic statistical theory²⁸. For cohort A, if p denotes the true tumor response rate with drug, the null and alternative hypotheses to be assessed in this trial are: $H_0: RR=p_0$ vs $H_1: RR=p_1$ ($p_0 < p_1$), with $p_0=0.15$ and $p_1=0.30$. To test these hypotheses, this trial is a k -stage single-arm design with $k=2$, being a Simon's 2-stage design¹. In this design with $k=2$, there are two analyses: a single interim (Stage 1) and a final (Stage 2) analysis. At the interim analysis, the response rate is evaluated in a fixed number (m) of patients using a predefined decision rule to determine if the study should stop for futility. If the study is not stopped for futility, a further fixed number of patients (l) are assessed for response, and a final analysis is performed on all ($m+l$) patients. In both interim and final analyses, the response rate will be presented together with the associated exact 90% CI.

With $p_0=0.15$ and $p_1=0.30$, the interim (Stage 1) analysis will be conducted with $m=22$ for efficacy patients (EE). If 3 or fewer responses are observed in these 22 patients, the cohort will be terminated in favor of the null for futility. Otherwise, a further 26 patients may be evaluated, for a total of 48 evaluable patients. If a total of 12 or more responses are seen in 48 evaluable patients (25%), then the null will have been rejected in favor of the alternative; otherwise, the null will not have been rejected.

Based on 500,000 trial simulations, this design provides an overall power of 80.1% to test the stated null and alternative hypothesis with a 1-sided Type I error rate of 0.049. Under the null, the probability of correctly stopping for futility at Stage 1 is 57.7%.

For cohort B and C, if p denotes the true tumor response rate with drug, the null and alternative hypotheses to be assessed in these cohorts are: $H_0: RR=p_0$ vs $H_1: RR=p_1$ ($p_0 < p_1$), with $p_0=0.05$ and $p_1=0.20$. To test these hypotheses, both B and C cohorts are the k -stage single-arm design with $k=2$, being a Simon's 2-stage design¹. In this design with $k=2$, there are three analyses: an interim analysis for Stage 1, an interim analysis for Stage 2 and a final analysis (for both Stage 1 and Stage 2). At the interim analysis (Stage 1), the response rate is evaluated in a fixed number (m) of patients using a predefined decision rule to determine if the study should stop for futility. If the study is not stopped for futility, a further fixed number of patients (l) are assessed for response at a second interim analysis (Stage 2). A final analysis is performed on all ($m+l$) patients at the time of study completion – see [Section 8.6](#) for details. For both interim analyses and final analysis, the response rate will be presented together with the associated exact 90% CI.

With $p_0=0.05$ and $p_1=0.20$, the interim (Stage 1) analysis will be conducted with $m=13$ for efficacy patients (EE). If 1 confirmed response is observed before the 13th patient has been followed-up for 24 weeks a subgroup of the DRC will meet to confirm continuation to Stage 2. If 0 responses are observed in these 13 patients, the cohort will be terminated in favor of the null for futility. Otherwise, a further 16 patients may be evaluated, for a total of 29 evaluable patients. Once 16 (EE) evaluable patients have been enrolled in Stage 2, an interim (Stage 2; once all patients have been treated and/or followed up for at least 12 months) analysis and a final analysis (at the time of study completion – see [Section 8.6](#) for details) will be performed. If a total of 4 or more responses (either at Stage 2 interim analysis or at final analysis) are seen in 29 evaluable patients

BerGenBio ASA
[name]
[name]
Norway

(13.8%), then the null will have been rejected in favor of the alternative; otherwise, the null will not have been rejected.

Based on 500,000 trial simulations, this design provides an overall power of 80% to test the stated null and alternative hypothesis with a 1-sided Type I error rate of 0.05. Under the null, the probability of correctly stopping for futility at Stage 1 is 51%.

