Cohort B will follow a k -stage single arm design with $k=2$, being a Simon's 2-stage design as above.

The rationale for a null hypothesis of $p_0=0.05$ is based on historic response rates to standard second and later line single agent chemotherapy such as docetaxel. In a phase III trial enrolling patients who had previously failed platinum-containing chemotherapy, 373 patients received either 100 mg/m² or 75 mg/m² docetaxel. An ORR of 10.8 and 6.7%, respectively, was observed in these patients³.

BerGenBio ASA
[name]
[name]
Norway

The ORR of pembrolizumab in combination with bemcentinib is expected to be at least as high as this in patients who progressed on first- or second line immune checkpoint inhibitor therapy.

With $p_0=0.05$ and $p_1=0.20$, the interim (Stage 1) analysis will be conducted with $m=13$ evaluable for efficacy patients (EE). If 1 confirmed response is observed after the 13th patient has been followed-up for 24 weeks, a subgroup of the DRC will meet to confirm continuation to Stage 2. If 0 responses are observed in up to 13 patients, the cohort will be terminated in favor of the null for futility. Otherwise, up to a further 16 patients may be evaluated (in Stage 2), for a maximum total of 29 (EE) evaluable patients. Once 16 (EE) evaluable patients have been enrolled in Stage 2, an interim analysis (Stage 2; once all patients have been treated and/or followed up for at least 12 months) and a final analysis (at the time of study completion – see [Section 8.6](#) for details) will be performed. If a total of 4 or more responses (either at Stage 2 interim analysis or at final analysis) are seen in up to 29 evaluable patients (13.8%), then the null will have been rejected in favor of the alternative; otherwise, the null will not have been rejected.

Up to 29 evaluable patients may therefore be enrolled to cohort B. It is expected that approximately 36 patients will be screened in order to identify 29 patients who meet all the inclusion and exclusion criteria and who are evaluable for response in cohort B.

Demographic and clinical characteristics at entry will be summarized using appropriate descriptive statistics. PD-L1 and Axl expression will be summarized for the ES.

Cohort C will be similar to cohort B in terms of size and design. It will follow a k -stage single arm design with $k=2$, being a Simon's 2-stage design as above.

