The rationale for a null hypothesis of $p_0=0.05$ is based on historic response rates to standard second line single agent chemotherapy such as docetaxel. In a phase III trial enrolling patients who had previously failed platinum-containing chemotherapy, 373 patients received either 100 mg/m² or 75 mg/m² docetaxel. An ORR of 10.8 and 6.7%, respectively, was observed in these patients⁴.

The ORR of pembrolizumab in combination with bemcentinib is expected to be at least as high as this in patients who progressed on first- or second line immune checkpoint inhibitor therapy.

With $p_0=0.05$ and $p_1=0.20$, the interim (Stage 1) analysis will be conducted with $m=13$ evaluable for efficacy patients (EE). If 1 confirmed response is observed after the 13th patient has been followed up for at least 24 weeks a subgroup of the DRC will meet to confirm continuation to Stage 2. If 0 responses are observed in up to 13 patients, the cohort will be terminated in favor of the null for futility. Otherwise, up to a further 16 patients may be evaluated, for a maximum total of 29 evaluable patients. Once 16 (EE) evaluable patients have been enrolled in Stage 2, an interim analysis (Stage 2; once all patients have been treated and/or followed up for at least 12 months) and a final analysis (at the time of study completion – see [Section 8.6](#) for details) will be performed. If a total of 4 or more responses (either at Stage 2 interim analysis or at final analysis) are seen in up to 29 evaluable patients (13.8%), then null will have been rejected in favor of the alternative; otherwise, the null will not have been rejected.

BerGenBio ASA
[name]
[name]
Norway

Up to 29 evaluable patients may therefore be enrolled to cohort C. It is expected that approximately 36 patients will be screened in order to identify 29 patients who meet all the inclusion and exclusion criteria and who are evaluable for response in cohort C.

Demographic and clinical characteristics at entry will be summarized using appropriate descriptive statistics. PD-L1 and Axl expression will be summarized for the ES.

Further details on the statistical methods and sample size can be found in [Section 8](#).

Schedules of Assessment and Pembrolizumab Administration Timing

[Table 3](#) summarizes the timing of pembrolizumab administration up to Cycle 35 (approximately 24 months of treatment) in relation to the timing of disease assessment.

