Cohort B will utilize a single-arm, Simon's 2-stage design with 2 interim analyses and a final analysis. The interim analysis for Stage 1 will be conducted for DRC review when 13 patients are evaluable (EE) for ORR. If 0 responses are observed in up to 13 (EE) patients, the cohort will be terminated in favor of the null hypothesis for futility, and no further participants will be recruited. When at least 1 patient has an observed response at the interim (Stage 1) analysis, up to a further 16 patients may be evaluated, for a total of 29 (EE) patients (see [Section 8.1](#)), taking the overall risk-benefit of the combination into consideration. The interim analysis for Stage 2 will be conducted once all patients have been treated and/or followed up for at least 12 months. The final analysis for cohort B will occur at the time of study completion – see [Section 8.6](#) for details. Cohort B will assess the anti-tumor activity and safety of bemcentinib when given in combination with pembrolizumab in patients with advanced adenocarcinoma of the lung with a maximum of one prior line of an anti-PD-(L)1 therapy (monotherapy).

Cohort C will utilize a single-arm, Simon's 2-stage design with 2 interim analyses and a final analysis. The interim analysis for Stage 1 will be conducted for DRC review when 13 patients are evaluable (EE) for ORR. If 0 responses are observed in up to 13 (EE) patients, the cohort will be terminated in favor of the null hypothesis for futility, and no further participants will be recruited. When at least 1 patient has an observed response at the interim analysis, up to a further 16 patients may be evaluated, for a total of 29 (EE) patients (see [Section 8.1](#)), taking the overall risk-benefit of the combination into consideration. The interim analysis for Stage 2 will be conducted once all patients have been treated and/or followed up for at least 12 months. The final analysis for cohort C will occur at the time of study completion – see [Section 8.6](#) for details. Cohort C will assess the anti-tumor activity and safety of bemcentinib when given in combination with pembrolizumab in patients with advanced adenocarcinoma of the lung with a maximum of one prior line of treatment with an anti-PD-(L)1 therapy in combination with a platinum-containing chemotherapy.

BerGenBio ASA
[name]
[name]
Norway

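### Section 8.1 gives 80% power for cohorts B and C and a one-sided alpha of 0.049 for cohort A; the printed decision rules give 83.8% and 0.045

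*Combined protocol and SAP*

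**What the plan says.** Section 8.1 fixes both two-stage rules completely.

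- **Cohort A:** null 15%, alternative 30%. Stop if 3 or fewer of 22 evaluable patients respond; otherwise add 26 and reject the null at 12 or more of 48. From 500,000 simulated trials the section reports an "overall power of 80.1% to test the stated null and alternative hypothesis with a 1-sided Type I error rate of 0.049", with a 57.7% chance of stopping at Stage 1 under the null.
- **Cohorts B and C:** null 5%, alternative 20%. "If 0 responses are observed in these 13 patients, the cohort will be terminated in favor of the null for futility"; otherwise add 16 and reject at 4 or more of 29. Also from 500,000 simulations, the section reports an "overall power of 80% to test the stated null and alternative hypothesis with a 1-sided Type I error rate of 0.05". It adds: "Under the null, the probability of correctly stopping for futility at Stage 1 is 51"%.

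The B/C rule is repeated elsewhere. Section 4 has "up to a further 16 patients may be evaluated, for a total of 29 (EE) patients". The Synopsis (Statistical Methods and Sample Size) says for cohort B that if 4 or more responses "are seen in up to 29 evaluable patients (13.8%), then the null will have been rejected in favor of the alternative", and says the same for cohort C.

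**The concern.** A two-stage binomial rule with its cut-offs and rates printed has exactly one power, one type I error and one stopping probability. Section 8.1 presents its figures as properties of the printed designs, so they should be reproducible. Two are not: B/C power and cohort A alpha.

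These sentences are where the plan states its error rates. If cohort B or C misses its cut-off, a reader will put the chance of having missed a true 20% response rate at 20%, when it is 16.2%. Cohort A's false-positive risk is shown as 4.9% when it is 4.5%. A figure that does not belong to its rule also raises the question whether a different design was simulated.

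**Working it through.** **Inputs**, all from Section 8.1, with n1 the Stage 1 size, r1 the stopping cut-off, n2 the Stage 2 size and R the total needed to reject:
- A: n1 = 22, r1 = 3, n2 = 26, R = 12, rates 0.15 and 0.30.
- B/C: n1 = 13, r1 = 0, n2 = 16, R = 4, rates 0.05 and 0.20.

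**Formula.** P(reject | p) = Σ over x > r1 of P(X1 = x) × P(X2 ≥ R − x), with X1 ~ Bin(n1, p) and X2 ~ Bin(n2, p). Null stopping probability = P(X1 ≤ r1 | p0).

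**B/C figures that reproduce.** Null stopping: 0.95^13 = 0.5133 (stated 51%). Alpha: 0.0512 (stated 0.05).

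**B/C power at p = 0.20:**

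| Stage 1 responses | Probability | Still needed of 16 | Probability | Product |
|---|---|---|---|---|
| 1 | 0.1787 | 3 | 0.6482 | 0.1158 |
| 2 | 0.2680 | 2 | 0.8593 | 0.2303 |
| 3 | 0.2457 | 1 | 0.9719 | 0.2388 |
| 4 or more | 0.2527 | 0 | 1 | 0.2527 |

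The sum is 0.8375 after rounding, against 80% stated. Type II error is 1 − 0.8375 = 0.1625 (0.16247 before rounding, so 16.2%). Under this rule 80% power is already reached at a true rate of 18.9%.

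**Cohort A, same formula:**

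| | Exact | Stated |
|---|---|---|
| Null stopping | 0.5752 | 57.7% |
| One-sided alpha | 0.0446 | 0.049 |
| Power | 0.7966 | 80.1% |

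A futility stop can only remove rejections. With none, alpha is P(Bin(48, 0.15) ≥ 12) = 0.0478. No Stage 1 futility rule combined with 12 of 48 can therefore give 0.049.

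**Could simulation error or rounding explain the gaps?** The standard error at 500,000 trials is √(p(1 − p)/500,000). Each gap is measured from the nearest value that rounds to the printed figure.
- B/C power: (0.83753 − 0.805)/0.00052 ≈ 62 SE.
- A alpha: (0.0485 − 0.04458)/0.00029 ≈ 13 SE.
- A power: (0.8005 − 0.7966)/0.00057 ≈ 7 SE. This is not noise either, but 0.4 of a point has no practical weight.
- A stopping: (0.5765 − 0.57518)/0.00070 ≈ 1.9 SE, consistent with noise.

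A fresh 500,000-trial simulation of the printed rules gave B/C power 0.8378 and A alpha 0.0448.

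**Do neighbouring designs give the stated figures?**

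| Design | Alpha | Power | Null stopping |
|---|---|---|---|
| B/C printed: 0/13, ≥4/29 | 0.051 | 83.8% | 51.3% |
| 0/13, ≥4/28 | 0.046 | 82.0% | 51.3% |
| 0/13, ≥4/27 | 0.042 | 80.1% | 51.3% |
| 0/10, ≥4/29 | 0.047 | 80.1% | 59.9% |
| A printed: 3/22, ≥12/48 | 0.0446 | 79.7% | 57.5% |
| 3/22, ≥12/49 | 0.0507 | 81.6% | 57.5% |
| 3/21, ≥12/49 | 0.0493 | 80.5% | 61.1% |

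None matches a full stated set. An exhaustive search (0.05 against 0.20, alpha at most 0.05, power at least 0.80, total up to 50) gives 0/10 with ≥4/29 as the optimal Simon design and 0/13 with ≥4/27 as the minimax. The printed B/C rule has the Stage 1 of the minimax design and the total of the optimal one.

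**Which rule is intended?** The rest of the plan supports the printed one: 4/29 = 13.8% (4/27 would be 14.8%), 13 + 16 = 29, 12/48 = 25%, and 48 + 29 + 29 = 106, the Synopsis total.

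**The case against.** The strongest reply is that nothing turns on these figures. The decisions are response counts, B/C has more power than stated, and A has a lower false-positive rate. That stands, and it limits the point to a correction of text.

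Second, 80% and 0.05 may be design targets, since the B/C sentence carries no decimals while the cohort A sentence does. This is possible, but the sentence attributes the 80% to simulation of this design. If it is a target, the text should say so and give the achieved power beside it.

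Third, the plan never claims an optimal or minimax design, so being neither is no defect, and the origin of the 80% cannot be established from the documents. That is right. The mixed-design explanation is only a possible source, and the repeated totals make the printed rule the likely intention.

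Fourth, calling the errors conservative covers only the two main figures. Correct restatement also shows B/C alpha at 0.051, just over 0.05, and cohort A power at 79.7%, just under 80%. This is fair, and the corrected text should show both openly.

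**Conclusion.** The concern holds. Under the printed rules B/C power is 83.8%, not 80% (3.8 points), and cohort A one-sided alpha is 0.045, not 0.049. The remaining figures agree at printed precision, lie within simulation error, or (cohort A power, 79.7% against 80.1%) differ immaterially.

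The calculation assumes only independent binomial responses, stopping rules applied as written, and exactly 22 then 48, or 13 then 29, evaluable patients. The only open question is which design was simulated. Confidence in the arithmetic is high. The consequence is a misreported pair of error rates, with no effect on conduct.

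**What to change.** 1. The sponsor's statistician identifies the design that was simulated and confirms that 3/22 then 12/48, and 0/13 then 4/29, are the intended rules.
2. If they are, keep every cut-off and sample size and correct two sentences in Section 8.1. For cohort A give power 79.7% and one-sided type I error 0.045. For cohorts B and C give power 83.8% and one-sided type I error 0.051. State that the last figure is marginally above 0.05 and that cohort A power is marginally below 80%. The stopping probabilities can stay.
3. Optionally, note that at exactly 4 of 29 the exact 90% confidence interval (4.9% to 28.8%) includes 5% although the count rule rejects, and that the count rule governs.

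The cost is one confirmation and two sentences.

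A minor, separate point can be settled at the same time. The Synopsis applies the 25% screen failure rate in two ways: 48/0.75 = 64 for cohort A, but 29 × 1.25 ≈ 36 for B and C and 106 × 1.25 ≈ 133 in total. The cohort figures sum to 64 + 36 + 36 = 136. State one base for the 25% and use it throughout.
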